8.1. Sample size determination

At the beginning of this study, we anticipated randomizing 140 patients with clinically node negative thyroid cancer, with the goal of 116 participants completing the study. Patients will be recruited from the Endocrine Surgery and Otolaryngology Clinics at the University of Wisconsin Hospitals and Clinics. This is a high volume tertiary care center with a large thyroid practice, performing approximately 350 thyroid operations per year. Thyroid cancer accounts for 30% of thyroidectomy cases at our institution and this is the pool from which the patients will be identified (approximately 105 patients/year). Approximately 15% of thyroid cancer cases will have a positive pre-operative ultrasound, thus decreasing our pool of eligible participants to approximately 89 patients per year. With an accrual goal of 140 participants within 4 years, we would need to recruit 39% of eligible patients each year.

Permanent complications in thyroid surgery are uncommon, but these complications can be disastrous for a patient that is affected. Permanent hypoparathyroidism occurs in 1-2% of patients after a total thyroidectomy and the risk may be as high as 14% when a CND is performed. The best surrogate marker to predict an increase in permanent morbidity is the incidence of transient hypoparathyroidism, which is substantially more common than permanent hypoparathyroidism. For example, transient hypoparathyroidism occurred in 12% of our last 270 patients undergoing a total thyroidectomy. The rate of transient hypoparathyroidism in patients treated with a CND has been shown in the literature to be significantly higher. The rate of transient hypoparathyroidism in recent large retrospective studies was reported to be between 38-51%.

We assumed a power of 0.8 and an alpha of 0.05. For sample size calculations we made the assumption that the incidence of transient hypoparathyroidism after a total thyroidectomy alone is 12% and that an increase to 36% (or tripling of the risk) is clinically significant. The rate of hypoparathyroidism in Arm 1 is based upon our last 270 patients and is a reliable estimate. The incidence in the CND arm is based on a

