review of the literature and we purposely chose a number on the lower end of quoted ranges to ensure that we are not underestimating our sample size. With these assumptions the sample size is 116, with 58 patients per arm. Due to the short follow up for our primary endpoint (post-operative day 1) and for our secondary endpoints (<12 months), we anticipate no significant loss to follow up. For our secondary aims, we chose the Dysphonia Severity Index (DSI) as representative and found a prior thyroid surgery study (45) showing that as few as 8 patients in a negative voice outcome group were sufficient to detect clinically meaningful differences on this measure versus patients with normal vocal functioning at 6 months post-op. Thus, the sample size in our study should be adequate to address our secondary aims even if there is attrition/ loss to follow-up.

The number of patients who must be consented will be larger than the final sample size because a portion of patients that are enrolled and evaluated pre-operatively may not be randomized the day of surgery (because malignancy is not proven intraoperatively, suspicious adenopathy is identified, or there is gross local invasion). We aim to increase the sample size by 20% to accommodate for this.

We have found in our examination of preliminary data that our objective measures are not effectively capturing the impact of surgery on patients and that the most critical and meaningful data that we are obtaining from our study is from the in-depth patient interviews. Given the value of our qualitative data, we need to ensure that we are capturing adequate qualitative data to identify differences between the objective and patient-reported evaluations of experiences with hypocalcemia and voice and swallowing problems caused by transient or permanent nerve injury. Ultimately, we plan to make our existing study aims even more robust by incorporating both objective and subjective data into each of our primary and secondary outcomes measures.

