Based on our experience with qualitative research and the rates of objective complications in the patients enrolled to date, we've determined that we need to enroll at least 62 patients in order to obtain an adequate dataset to examine the impact of hypocalcemia and 70 patients in order to obtain an adequate dataset to examine the impact of vocal cord dysfunction. While we will continue to recruit as many patients as feasible, based on these calculations, if we are able to enroll at least 70 patients, this should give us the data necessary to evaluate all of our study aims.

Therefore, we will plan to randomize 70 - 140 patients. We will plan to recruit patients up until year 5 of the study as the primary recurrence endpoint will be at 1 year. Given the fact that we anticipate having at least 89 eligible patients per year, we should meet our recruitment goal while allowing for at least 1 year of follow up in all study patients.

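### Section 8.1 declares 70 patients enough for every study aim without giving power at 70; at 35 per arm, power for its own 12% vs 36% target is about 55% to 66.5%, not 80%

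*Combined protocol and SAP*

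**What the plan says.** Section 8.1 contains one quantitative sample size argument for a comparison between arms. It takes transient hypoparathyroidism as 12% after total thyroidectomy alone and treats a rise to 36% as clinically significant. "We assumed a power of 0.8 and an alpha of 0.05", it says, and it concludes: "With these assumptions the sample size is 116, with 58 patients per arm". The same section identifies post-operative Day 1 as the time of the primary endpoint. The accrual plan at the start was 140 randomised, "with the goal of 116 participants completing the study".

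The section then reports that the objective measures are not capturing the impact of surgery well and that the interviews are the most informative data. It continues: "Based on our experience with qualitative research and the rates of objective complications in the patients enrolled to date", the investigators concluded that "we need to enroll at least 62 patients in order to obtain an adequate dataset to examine the impact of hypocalcemia", and that 70 are needed for vocal cord dysfunction. From this it draws the general statement that "if we are able to enroll at least 70 patients, this should give us the data necessary to evaluate all of our study aims", and then: "Therefore, we will plan to randomize 70 - 140 patients".

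No power, detectable difference or new target rate accompanies 62 or 70. Section 8.2 still plans comparisons between the two randomised groups for all primary aims, with an unspecified experiment-wise alpha adjustment. Section 9.1 still describes a difference in complication frequency between the arms as the primary aim.

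**The concern.** A statement that covers all study aims covers the primary one. The only calculation for that aim needs 116 patients, and 70 is 70/116 = 60% of that. The target difference was not changed when the floor was lowered, so the same section asks for 116 and calls 70 sufficient for the same comparison.

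The trial's hypothesis is that adding prophylactic central neck dissection raises the complication rate. If accrual ends near the floor, a non-significant Day 1 result would be quite likely even if the risk had truly tripled. A reader could then cite the protocol's own assurance that 70 was enough and take the result as evidence that the dissection is safe.

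**Working it through.** **Inputs (all section 8.1).** p1 = 0.12, p2 = 0.36, difference d = 0.24, alpha 0.05, power 0.80, equal arms, no significant loss to follow-up. Test and sidedness are not stated; two-sided is assumed unless noted. No experiment-wise adjustment is applied unless noted.

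**Step 1: reproduce 116.** With the mean rate 0.24, 2 × 0.24 × 0.76 = 0.3648 and 0.12 × 0.88 + 0.36 × 0.64 = 0.3360.

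- Uncorrected: n = (1.960 × √0.3648 + 0.842 × √0.3360)² / 0.24² = 48.5, so 49 per arm (98 in total).
- Continuity-corrected: n = (48.5/4) × [1 + √(1 + 4/(48.5 × 0.24))]² = 56.5, so 57 per arm (114 in total).
- One-sided versions give 39 per arm (78) or, corrected, 47 per arm (94).

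The two-sided corrected formula comes within two patients of 116. The stated size is sound.

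**Step 2: the same formula at 35 per arm.** Power = Φ{[d − 1/n − 1.960 × √(0.3648/n)] / √(0.3360/n)}.

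- n = 35: (0.24 − 0.0286 − 0.2001)/0.0980 = 0.116, power 0.546.
- n = 58: (0.24 − 0.0172 − 0.1554)/0.0761 = 0.884, power 0.812.

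**Step 3: exact power.** Sum the binomial probabilities of all outcome pairs that the test declares significant (two-sided 0.05, 12% vs 36%).

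| Per arm | Corrected formula | Fisher | Pearson |
|---|---|---|---|
| 31 (the 62 figure, if all randomised) | 0.481 | 0.509 | 0.620 |
| 35 (the floor of 70) | 0.546 | 0.568 | 0.665 |
| 58 (the 116 design) | 0.812 | 0.830 | 0.880 |
| 70 (the ceiling of 140) | 0.888 | 0.897 | 0.931 |

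Power of 80% is first reached at 48 per arm (Pearson), 55 (Fisher) or 57 (corrected formula), that is 96 to 114 patients.

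**Step 4: sensitivity at 35 per arm.**

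- One-sided 0.05: 0.671 (corrected formula), 0.689 (Fisher), 0.774 (Pearson). All are below 0.80.
- Alpha halved to 0.025 (an assumed example of the section 8.2 adjustment, which is not specified): 0.430, 0.466, 0.568.
- Higher rate with dissection, Fisher to Pearson: 0.64–0.73 at 38%, 0.82–0.88 at 44.5% (midpoint of the cited 38–51%), 0.93–0.96 at 51%. Reaching 80% needs about 41% (Pearson) to 44% (Fisher).

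**Step 5: what the floor means in practice.** With 4/35 events in Arm 1, significance needs 11/35 (Pearson) or 12/35 (Fisher) in Arm 2. That is an observed difference of 7/35 = 20 or 8/35 = 23 points, against a target of 24. With 7/58 it needs 16/58 or 17/58, which is 16 or 17 points. The 95% half-width on the difference, 1.96 × √(0.3360/n), is 19 points at 35 per arm and 15 at 58.

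**Step 6: is 35 per arm guaranteed?** Section 3 (Operative Procedure) enrols a patient when the randomisation envelope is opened; section 7 enrols at consent. The Summary and section 1.2 spread 70–140 over three arms, one of them not randomised, while section 8.1 randomises 70–140. If 70 includes non-randomised patients, there are fewer than 35 per arm. As an illustration, suppose 70 counted consented patients and the section 8.1 allowance ("We aim to increase the sample size by 20% to accommodate for this") applied. Then 70/1.2 ≈ 58 would be randomised, 29 per arm, with power 0.447 (corrected formula), 0.464 (Fisher) or 0.581 (Pearson).

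**The case against.** **No stated figure is wrong.** The 116 reproduces, and the protocol does not claim 80% power at 70. This stands: the fault lies in what the adequacy sentence covers.

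**Seventy is a minimum.** The section says recruitment will continue as far as feasible, and power passes 80% within the 70–140 range. The shortfall is therefore confined to the lower part of the range, but the sentence declares that lower part sufficient.

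**The 36% target is conservative.** It was deliberately set below the cited 38–51%, and at the midpoint of that range 35 per arm would be enough. This softens the point but does not remove it. Section 8.1 also calls 36% clinically significant and chose it to guard against too small a sample; relying on a higher rate at 70 gives up that guard without saying so. At 38% power is still only 0.64–0.73.

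**The 55% comes from a planning formula.** Correct: the exact tests give about 57% and 66.5%, so the miss rate for an actual test is about 43% or 33.5%, rather than 45%. The conclusion is unaffected.

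**The primary objective is broader than one binary test.** Section 2.1 lists several measures, and section 8.1 now wants interview data within each outcome. Power for the continuous measures was not examined here. Even so, section 8.1 ties the primary endpoint to Day 1, and section 8.2 keeps testing between arms.

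**Section 8.1 itself says that 70–140 will be randomised.** Read alone, that supports 35 per arm and makes the 29-per-arm case an illustration only. The conflict with the Summary and section 1.2 remains.

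**Conclusion.** The concern holds. Section 8.1 presents 70 patients as adequate for all aims, including a primary comparison for which its own unrevised assumptions require 116. At 35 per arm, two-sided 0.05, power for 12% vs 36% is 56.8% (Fisher) or 66.5% (Pearson); by the method closest to reproducing 116 it falls from 81.2% to 54.6%. It is below 80% under every test and sidedness tried.

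These figures assume equal arms, all patients randomised and evaluable, and no alpha adjustment. Fewer randomised patients or an adjusted alpha would lower them; a rate with dissection above about 41% to 44% would bring power to 80%. The point must be fixed because it concerns what the protocol tells readers about its primary comparison.

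**What to change.** 1. In section 8.1, tie the 80% power to the 116-patient calculation. Add the power at 70 randomised for 12% vs 36%: about 57% (two-sided Fisher), 66.5% (two-sided Pearson) or 55% (continuity-corrected formula). Name the test and sidedness, and say that the figure precedes any section 8.2 adjustment.
2. Limit the 70-patient sentence to adequacy of the qualitative data and remove its reach over all aims. Commit to reporting the Day 1 risk difference with its 95% confidence interval at whatever size is reached, and state that a non-significant result will not be read as no difference.
3. Define enrolment once. Reconcile the Summary and section 1.2 (70–140 across three arms) with section 8.1 (70–140 randomised). Within section 8.1, reconcile 140 randomised with 116 completing against a 20% increase for patients who are never randomised (116 × 1.2 = 139.2).
4. Do not rely on the section 8.1 precedent of 8 patients with poor voice outcome to show adequacy between arms: it compares poor-voice with normal-voice patients. If a detectable difference is given instead (about 0.68 SD at 35 per arm, 80% power, two-sided t-test), label it a Day 12 figure assuming complete data. Later voice evaluations follow only an abnormal one, and evaluations may be waived.

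The cost is protocol wording and a less favourable stated power at the floor. No patients or procedures are added. The rewording adds no power; it stops the text from claiming an adequacy that was not calculated.

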Interviews (Audio Recorded)	X			X	X		X	X	
Participant Receives Symptom Log ^{3, 12}	X ^{3, 12}								
Randomization ¹³	X ¹³								
Enrolled	X								
Adverse Events Monitoring	X		X	X			X	X	
Endocrine Consult ¹⁴			SOC ¹⁴						
Participant Returns Symptom Log & it is Reviewed ³			X ³						
Participant & Study Staff Unblinded			X						
Unstimulated Thyroglobulin ¹⁵				SOC ^{15, 16}			SOC ¹⁵	SOC ¹⁵	
Stimulated Thyroglobulin ¹⁵					SOC ^{2, 15}	SOC ¹⁵	SOC ¹⁵	SOC ¹⁵	
Radioactive iodine (RAI) Whole Body Scan ²					SOC ²		CI ⁴		
QI follow-up survey is administered via email									X

Procedure Key: **SOC** = performed as needed per Standard of Care; **X** = Research Only; **CI** = Clinically Indicated (performed SOC if warranted by patient's condition, otherwise the procedure will be done as part of research)

¹The Month 6 time point must occur at least 4 weeks after the RAI is given, if applicable.

²Patients with an elevated unstimulated thyroglobulin level (>2 ng/mL) at Week 6 and/or an intermediate or high risk level will be evaluated for standard of care radioactive iodine ablation therapy and corresponding TSH stimulated thyroglobulin lab and radioactive iodine whole body scan.

³Only patients who receive at least a total thyroidectomy (e.g. total thyroidectomy with central neck dissection, total thyroidectomy with lateral neck dissection)

⁴If Thyroglobulin >2ng/ml and neck US is negative (**randomized patients only**)

⁵All participants will be asked to stop their calcium and calcitriol supplementation 12 hours prior to their follow up appointment(s) so that a repeat calcium and PTH level can be checked.

⁶Vitamin D is clinically indicated if PTH is elevated or calcium is low.

⁷Ultrasounds within three months of surgery can be used for screening purposes.

⁸CXR only performed as needed at screening to rule out metastases.

⁹Voice evaluations are routinely performed pre-operatively in patients with prior neck surgery or voice complaints and post-operatively in anyone with a voice concern.

¹⁰Evaluations will only be obtained if results are abnormal at previous evaluation.

¹¹Swallow studies were eliminated as of 12/01/2016.

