1.2. Rationale and hypothesis

We propose a clinical trial in which 70 - 140 patients undergoing surgery for PTC with no pre-operative evidence of distant metastasis will be enrolled into one of three treatment arms: total thyroidectomy with prophylactic central neck dissection, total thyroidectomy without central neck dissection or standard of care. The total thyroidectomy patients will be randomized into one of the first two arms. The standard of care patients, patients who are not eligible for the randomization arms pre-operatively or are unable to be randomized intraoperatively, will be enrolled into the third study arm and will not have any aspect of their cancer care modified by study participation but will otherwise follow the same follow up study assessment schedule as the patients in the randomization arms. In the absence of this clinical trial, patients seen at our center would be offered a total thyroidectomy without central neck dissection, which is our current practice standard. At many other major academic centers, however, a prophylactic central neck dissection is the standard of care. Currently about 50% of high volume institutions are doing a central neck dissection routinely in their practice. While performing a central neck dissection may increase the risks of surgery it may also decrease the risk of recurrence. We do not know, given the presently available data, which will be greater, and therefore this study has true clinical equipoise.

Our hypothesis is that total thyroidectomy with prophylactic central neck dissection will result in a higher complication rate in comparison with total thyroidectomy alone for papillary thyroid cancer.

2. Objectives

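### Section 8.1 sets an open 70-140 range after outcome data were examined, with no outcome-independent rule for stopping inside it, no sequential alpha control and no power restated at 70

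*Combined protocol and SAP*

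**What the plan says.** Section 8.1 gives the design assumptions: "We assumed a power of 0.8 and an alpha of 0.05", with transient hypoparathyroidism at 12% after total thyroidectomy alone and 36% with central neck dissection (CND). These lead to 116 patients, 58 per arm. The accrual figure of 140 goes with an allowance of 20% for patients who are not randomised on the day of surgery.

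The same section then reports a look at the data: "We have found in our examination of preliminary data that our objective measures are not effectively capturing the impact of surgery on patients". It sets new minimums of 62 patients (hypocalcaemia) and 70 (vocal cord dysfunction), "Based on our experience with qualitative research and the rates of objective complications in the patients enrolled to date". The result is: "Therefore, we will plan to randomize 70 - 140 patients". On how the final number will be reached, it says "While we will continue to recruit as many patients as feasible" and gives year 5 as the limit of recruitment.

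On knowledge of arm, Section 3 (Blinding) says the surgeon is never blinded and participants are unblinded at the Day 12 appointment. The schedule of activities has a row "Participant & Study Staff Unblinded". Section 8.1 places the powered endpoint at post-operative day 1.

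On error control, Section 8.2 says only that experiment-wise error will be handled by an appropriate alpha adjustment. Section 7.5 lets the DSMC ask for suspension on safety grounds and gives no statistical boundary.

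**The concern.** A sample size that can fall anywhere between 70 and 140 is harmless if the stopping point has nothing to do with the arm comparison. It is not harmless if recruitment can end when the difference looks convincing and continue when it does not. Then a nominal 5% test no longer has a 5% error rate, and the nominal confidence interval undercovers.

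The plan leaves that possibility open. The target has already been changed once after outcome data were seen. The day 1 endpoint is available early, and arm becomes known patient by patient during accrual. Any stop from 70 onward complies with the protocol. Section 11.1 also describes regular meetings at which each subject's results are discussed, for the class of trial that generally includes institutional Phase II studies, and nothing separates that discussion from the recruitment decision. A reader of a positive harm result at, say, 84 patients could not rule out optional stopping from the protocol.

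A second consequence does not depend on anyone's conduct. The minimum of 70 rests on adequacy of the qualitative data and on complication rates to date, and the power of the arm comparison was not recalculated for it.

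**Working it through.** **1. The plan's own figure.** Inputs from Section 8.1: p1 = 0.12, p2 = 0.36, alpha 0.05, power 0.80, equal arms. Sidedness is not stated, and two-sided is assumed. With mean rate 0.24:

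n = [1.960 × √(2 × 0.24 × 0.76) + 0.842 × √(0.12 × 0.88 + 0.36 × 0.64)]² / 0.24² = [1.960 × 0.6040 + 0.842 × 0.5797]² / 0.0576 = 48.5, so 49 per arm.

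With the continuity correction: (48.5/4) × [1 + √(1 + 4/(48.5 × 0.24))]² = 56.5, so 57 per arm and 114 in total. This is within 2 patients of the stated 116, so the figure is reproduced. Also 116 × 1.2 = 139.2, which gives the 140.

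**2. Power at the new minimum.** With 35 per arm:

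z = (0.24 × √35 − 1.960 × 0.6040) / 0.5797 = (1.420 − 1.184) / 0.5797 = 0.41, so power is 66%.

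Exact enumeration gives 66% for the chi-square test and 57% for Fisher's exact test. At 58 per arm the exact values are 88% and 83%.

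**3. Type I error if N does not depend on arm results.** With N drawn at random from 70-140, independently of the outcome, simulated type I error is 4.97%. There is no inflation.

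**4. Type I error if stopping followed unadjusted by-arm tests.** Simulation under equal arms (true rate 12%, 24% or 36% for binary data), stopping at the first two-sided p below 0.05 between 70 and 140. The look schedules are assumptions; the documents give none.

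| Looks between 70 and 140 | Normal theory | Chi-square | Fisher |
|---|---|---|---|
| 70 and 140 (2 looks) | 8.2% | 8.3-9.0% | 3.9-5.3% |
| every 10 patients (8 looks) | 12.2% | 12.5-12.9% | 6.1-8.1% |
| every 2 patients (36 looks) | 14.6% | 14.1-14.8% | 6.7-9.7% |

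A look after every patient (71 looks) gives 15.2% under normal theory. The Fisher column starts low because that test is conservative: a single look has an error rate of 1.7-3.3%.

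**5. Early stopping only for CND harm.** If recruitment stopped early only when CND looked worse, with an ordinary two-sided test at 140 otherwise, normal theory gives 6.6% (2 looks), 8.6% (every 10) and 9.8% (every 2). This matches the directional hypothesis in Section 1.2, that adding CND "will result in a higher complication rate in comparison with total thyroidectomy alone".

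**6. What a correction would look like.** Constant critical values that hold overall two-sided error at 0.05 are |z| of about 2.18 for looks at 70 and 140 and about 2.36 for looks every 10 patients. Neither counts the preliminary examination, which would have to be added if it was by arm.

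**The case against.** The strongest reply is that the inflation figures price a practice the documents do not describe. Section 8.1 names feasibility and year 5 as what governs the final number. Nowhere does the plan mention by-arm significance tests or stopping when a difference appears. The reason given for the change points away from chasing a positive result: the objective measures were thought uninformative, and the minimums were set by the needs of the qualitative work. Complication rates to date could have been pooled, which would cause little or no inflation. Knowing each patient's arm is also not the same as compiling outcome tables by arm.

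All of this stands. A reader might infer that the team saw the arm difference, or that the trial's false-positive rate is 8-15%. The documents support neither inference. That range also needs a chi-square or normal test, and Section 8.2 names no test for the binary day 1 endpoint. With Fisher's exact test and two looks there is essentially no excess over 5%.

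It would also be too strong to say that the plan has no alpha control, because Section 8.2 promises an adjustment. What can be said is that the adjustment has no stated method and is not linked to looks or to a variable sample size. Likewise, 0.05 appears as a sample-size assumption, and 140 was an anticipated number and not a binding target.

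The objection does not supply the missing rule. Recruiting as many as feasible until year 5 states an intention, while the 70-patient floor permits an earlier stop for any reason. Nor does the objection touch the loss of power at 70.

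**Conclusion.** The concern holds as a gap in the plan, with a conditional size. Section 8.1 moved from an anticipated 140 to an open range after outcome data were examined, and nothing makes the stopping point independent of arm results while arm is known during accrual.

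Type I error is about 5% if accrual or the calendar decides. It could be about 8-15% with a chi-square or normal test, about 4-10% with Fisher's exact test, or about 7-10% with early stopping for CND harm only, if unadjusted by-arm tests decided. These figures assume equal allocation, two-sided 0.05 tests and the look schedules shown.

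The loss of power is firmer: about 57-66% at 70 patients for the plan's own effect. It assumes only the plan's event rates, two-sided testing and all 70 patients analysed. The documents do not establish that error was in fact inflated.

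**What to change.** In Section 8.1:

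- State that recruitment ends at the earlier of 140 randomised or the planned end of recruitment in year 5.
- State that outcome data by arm are not used for that decision and go only to the DSMC, whose safety authority is unchanged.
- State whether the preliminary examination was by arm or pooled.
- Restate power for 12% versus 36% at the 70-patient minimum, about 57% (Fisher) to 66% (chi-square), since recruitment could still close with only 70 randomised.

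Only if by-arm results did or may influence stopping, add to Section 8.2 a spending function for the primary endpoint that counts every look, including the preliminary one.

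The cost is protocol wording, with no extra patients required. The team gives up discretion over when to stop within the range or, if it keeps that discretion, accepts a slightly stricter threshold.
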